1.0 Background

Many pregnancy complications, including growth restriction, preterm birth and stillbirth, are associated with inflammation in the placenta, which is currently diagnosed after delivery. This non-infectious placental inflammation is known as villitis of unknown etiology (VUE) is characterized by maternal T cells infiltrating into the placenta and causing destruction of the villous architecture. However, it's not known what leads to these maternal T cells becoming activated against fetal cells, nor it is understood whether VUE is a cause or an effect of the associated fetal complications. The main challenge faced by researchers studying VUE is that there are no strategies to predict VUE *in utero*.

1.1 Villitis of Unknown Etiology

Intrauterine growth restriction (IUGR) appears to be associated with a placental pathology called villitis of unknown etiology (VUE).¹ During VUE, maternal T cells are found at high levels in the chorionic villi, causing destruction of placental architecture without clinical signs and symptoms of maternal (or fetal) infection.² VUE is diagnosed in 30% of all placentae.³ However, exact prevalence and the significance of this diagnosis, along with its potential role in IUGR, remains unknown. As half of a fetus' genetic material is paternally derived, VUE may represent a rejection response by the maternal immune system. Human leukocyte antigens (HLA), which are critical to the success of organ transplantation, may provide novel insights into VUE. Our published work identified that HLA class I and II receptors are upregulated in placentae with VUE compared to unaffected, gestational age-matched controls.⁴ Additionally, HLA-typing of VUE affected mothers and their newborns demonstrated increased HLA-mismatch compared to unaffected pairs.⁴ Our follow-up data (in review) utilizing T cell receptor spectratyping shows a significant expansion of T cell clones in placentae with VUE compared to controls; however, these clones are unique to each subject further indicating VUE is not a response to a shared antigen (as with an undetected infection).

1.2 Ultrasound Imaging

The scientific premise for this project is supported by strong animal data out of John Hopkins. This group utilized *in utero* Doppler ultrasound to identify intrauterine inflammation in a mouse model. Pregnant mice injected with lipopolysaccharide into the uterine cavity have intrauterine inflammation, which researchers found to cause elevated resistance indices, pulsatility indices and a greater occurrence of absent end-diastolic flow in the umbilical and uterine arteries.⁵ Women diagnosed with fetal IUGR during pregnancy will undergo Doppler ultrasound to monitor signs of fetal health. Inflammation is also associated with abnormal growth of microvessels.^{6,7} Current Doppler technology is not sensitive enough to detect these microvessels, whereas the new microvessel imaging technology can detect these small changes in blood flow.^{8,9} Therefore, as microvessel change is associated with inflammation, and inflammation is related to VUE and its associated fetal complications, we believe combining Doppler imaging with microvessel imaging will provide more power to identify placental villitis, possibly even those cases of mild villitis. Additionally, we will measure the ultrasound attenuation coefficient (UAC) in the placenta¹¹, which would provide information on fat fraction that may be a useful evaluation of placenta health.

Study Plan: This study will collect:

1. Ultrasound measures during the third trimester (>28 weeks)
2. Clinical placental specimen after birth
3. Patient demographics from the electronic medical record

Studies utilizing these three things will be performed as described in the sections that follow.

2.0 Goals

We aim to develop an ultrasound method to identify VUE induced inflammation in the human placenta during gestation. We hypothesize that hemodynamic changes can also be observed in the human placenta diagnosed with VUE by conventional Doppler ultrasound and microvessel imaging (also called 3D imaging in the consent form).

2.1 Primary

3.11 Our goal is to determine whether Doppler ultrasound measures of blood flow can predict VUE during gestation in a cohort of growth restricted fetuses compared to normal controls.

2.2 Secondary

2.12 We aim to measure differences in microvessel imaging to determine if it can provide stronger evidence for VUE diagnosis.

3.0 Patient Eligibility

3.1 Registration – Inclusion criteria IUGR cohort:

3.11 Age ≥ 18 and ≤ 45 years at study entry.

3.12 Diagnosis of IUGR before admission to labor and delivery.

3.14 Ability to provide written informed consent.

3.16 Weight greater than 110 pounds (50 kilograms, a standard requirement in obstetrics studies that include blood draws).

3.17 >28 weeks gestation

3.2 Registration – Inclusion criteria control cohort:

3.21 Age ≥ 18 and ≤ 45 years at study entry.

3.22 No known pregnancy complications at obstetrics visit (+/- 1 week gestational age of IUGR cohort)

3.23 Ability to provide written informed consent.

3.24 Weight greater than 110 pounds (50 kilograms, a standard requirement in obstetrics studies that include blood draws).

3.25 >28 weeks gestation

3.3 Registration – Exclusion criteria

3.31 Known immunodeficiency

3.32 Chronic, active viral infections, including HIV-1/2, HTLV-1/2, hepatitis B/C.

- 3.33 Known autoimmune disease (e.g., rheumatoid arthritis or systemic lupus erythematosus)
- 3.34 Solid organ or transplant recipient.
- 3.35 Multiple gestations.
- 3.36 Not planning on delivering at Mayo Clinic
- 3.37 Ruptured membranes
- 3.38 <28 weeks gestation

4.0 Test Schedule

Tests and procedures	At registration (3 rd trimester diagnosis of IUGR +/- 1 week for all controls)
Maternal and fetal demographics ¹	X
Ultrasound imaging	X
Clinical placenta specimen collection ²	X

1. Abstracted from the medical record.
2. Placenta pathologic sampling and review per clinical protocol

5.0 Grouping Factor: None.

6.0 Registration/Randomization Procedures

- 6.1 Participants will be recruited from patients obtaining antenatal care for pregnancy in the obstetrics clinic at Mayo Clinic in Rochester, Minnesota. Women who meet the eligibility criteria (see above) will be offered the opportunity to participate in the study. Informed consent will be obtained prior to enrollment.

7.0 Protocol Intervention

This study will take place in the Rochester Methodist Hospital and will enroll women attending antenatal care through the Department of Obstetrics and Gynecology. Annually, 2500 women receive care and deliver at the Mayo Clinic Family Birth Center. This study will consist of two cohorts: 1) women diagnosed with intrauterine growth restriction (IUGR) and 2) women having uncomplicated pregnancies. Forty women will be enrolled after being diagnosed with IUGR. Based on our clinical data we expect 50% to have a VUE diagnosis. Another cohort of 20 women having uncomplicated pregnancies will be enrolled, matched on gestational age at ultrasound and fetal sex.

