7.1 Study Methodology

Following consent, women will undergo a comprehensive Doppler ultrasound of the placenta. Prenatal ultrasound is routinely used in clinical practice and considered safe. The ultrasound output level used in this study will be below the FDA limit for fetal imaging. Ultrasound measures to be collected include uterine artery (UtA) and

umbilical artery (UA), systolic/diastolic (S/D) ratio, resistance index (RI), pulsatility index (PI) and presence of early diastolic notch will be collected for each subject.

Additionally, we will explore the benefit of novel ultra-sensitive Doppler technology for microvessel imaging of the placenta. This technology can substantially improve small vessel imaging on ultrasound. A Verasonics ultrasound scanner will be used for ultra-sensitive Doppler imaging. We will collect data on vessel density, periphery-to-center vessel density ratio (VDR), microvessel morphology and the ultrasound attenuation coefficient (UAC). Relevant information about the Verasonics scanner can be found in the Device section.

Maternal and fetal demographics will be collected for all study subjects. Statistical differences between variables in our three groups will be determined ANOVA by Kruskal-Wallis tests if normality is not met. Significance will be defined as a p-value ≤ 0.05 .

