7.2 Pathologic Review

In order to confirm VUE diagnosis, placentae will be collected after delivery and placed in formalin. A minimum of 6 samples will be obtained, 2 from cord and membranes and 4 from parenchyma. Placental tissue from the control cohort will then be processed and embedded into paraffin blocks (FFPE) for pathological review for the research study. Placental tissue from the IUGR cohort will be processed and embedded into paraffin blocks (FFPE) for pathological review as per standard clinical pathology protocols. Blocks will be prepped and stained with hematoxylin and eosin for histologic examination by our expert pathologist, [name]. All diagnoses will be based on established and published criteria from the Amsterdam Placental Workshop Group and Society for Pediatric Pathology.¹⁰ Severity, based on immune cell infiltration into the placenta, will be correlated back to ultrasound findings and pregnancy outcome. We will also share de-identified FFPE blocks collected for research only (not clinical residual tissues) with Alpenglow. Alpenglow Biosciences is located in One Discovery Square – Advanced Diagnostics Laboratory. The team will test whether their 3D histology technique can work for placental vascular evaluation (feasibility study).

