15.0 Statistical Considerations and Methodology

15.1 This is a feasibility study; therefore, no formal power analysis was completed

A total of 61 women will be accrued; 40 with a diagnosis of IUGR and 20 gestational age matched controls (+/- 1 week) will be analyzed. These women must be undergoing obstetric care for their pregnancy at Mayo Clinic. We are not offering remuneration; however, based on our previous studies we had a high recruitment and retention rate.

All statistical analyses will be performed using JMP version 10.0 (SAS Institute). Data will be examined for normality using the Shapiro-Wilk test, and between-group differences in expression for each ultrasound measure in our three groups will be analyzed with the nonparametric Kruskal-Wallis tests (non-parametric) or ANOVA (parametric). Dunn's method will be utilized to correct for multiple comparison testing. P-values <0.05 will be considered statistically significant.

Principal component analysis (PCA) will be used to assess the ability of the biomarker panel to separate individual data points (score plot) by projection of the original data on the first two principal components (PC1 and PC2), as well as correlations among ultrasound measures (loading plot). This will reduce the complexity of multidimensional data models by linearly combining multiple factors and downsizing them into new variables or principal components while retaining the original information.

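### The planned group tests ignore gestational age at ultrasound, which matching controls cannot balance between VUE-positive and VUE-negative IUGR women; a supporting adjusted model would be a cheap improvement

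*Combined protocol and SAP*

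**What the plan says.** Section 7.0 plans 40 women with IUGR and 20 with uncomplicated pregnancies, the latter "matched on gestational age at ultrasound and fetal sex". Sections 3.2, 4.0 and 15.1 give the GA match as within 1 week. On the IUGR cohort, section 7.0 adds: "Based on our clinical data we expect 50% to have a VUE diagnosis".

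IUGR women are scanned at registration, which section 4.0 ties to the third-trimester IUGR diagnosis. Section 3.1 admits them from above 28 weeks and states no upper limit. VUE status comes later, under section 7.2: "In order to confirm VUE diagnosis, placentae will be collected after delivery".

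For the analysis, section 15.1 says that "between-group differences in expression for each ultrasound measure in our three groups will be analyzed with the nonparametric Kruskal-Wallis tests" or by ANOVA, with Dunn's method for multiple comparisons, and then describes a principal component analysis. Section 7.1, directly after its sentence on demographics, says: "Statistical differences between variables in our three groups will be determined ANOVA by Kruskal-Wallis tests if normality is not met". Neither section names a covariate, a stratification, a GA-standardised value or a matched analysis. Section 7.3 collects fetal sex and GA at sample collection, but does not name GA at ultrasound. Section 15.1 also states: "This is a feasibility study; therefore, no formal power analysis was completed".

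**The concern.** The plan treats GA at scan and fetal sex as important enough to match on, then leaves both out of the analysis. For IUGR women against matched controls the cost is precision. For VUE-positive against VUE-negative IUGR women the matching does nothing: both groups come from the same unmatched cohort and are separated only once the placenta has been examined. The sponsor's own published comparison, described in section 1.1, found HLA receptors "upregulated in placentae with VUE compared to unaffected, gestational age-matched controls"; this plan has no counterpart for the comparison within IUGR.

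That comparison is the one that separates a VUE signal from an IUGR signal. If the two groups happen to be scanned at different gestations, and a measure changes with gestation, the unadjusted test could show a VUE difference that is really a GA difference, or hide a real one. The result could misdirect the choice of which measures to pursue.

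**Working it through.** **The plan's own figure.** There is no power calculation to reproduce. The only group size that follows from the text is 40 × 0.50 = 20 expected VUE-positive IUGR women, leaving 20 VUE-negative (95% binomial range for VUE-positive: 14 to 26).

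**Inputs that are assumed, because the documents do not give them.**
- GA at scan uniform over 28-40 weeks, so SD = 12/√12 = 3.46 weeks.
- Share of a measure's variance explained by GA: R² = 0.04, 0.10, 0.25 or 0.40.
- Bonferroni over three pairs, 0.05/3 = 1.7% two-sided, standing in for Dunn's method.
- Controls matched within 1 week and on sex to randomly chosen IUGR women.

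**Bias from a gap.** With slope √R²/3.46 SD per week, a 2-week gap shifts the unadjusted difference by 2 × √R²/3.46:
- R² 0.04: 2 × 0.200/3.46 = 0.12 SD
- R² 0.10: 2 × 0.316/3.46 = 0.18 SD
- R² 0.25: 2 × 0.500/3.46 = 0.29 SD
- R² 0.40: 2 × 0.632/3.46 = 0.37 SD

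**Simulation, VUE-positive v VUE-negative** (20,000 trials per setting). The ANOVA contrast is compared with the same model plus GA and sex.

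| R² | 0.04 | 0.10 | 0.25 | 0.40 |
|---|---|---|---|---|
| False positives, 1-week gap, unadjusted | 1.8% | 2.1% | 2.8% | 3.3% |
| False positives, 2-week gap, unadjusted | 2.3% | 3.4% | 6.5% | 9.5% |
| False positives, 2-week gap, adjusted | 1.6% | 1.5% | 1.5% | 1.6% |
| Power at 0.8 SD, no gap, unadjusted | 53% | 52% | 53% | 53% |
| Power at 0.8 SD, no gap, adjusted | 53% | 56% | 66% | 77% |
| Power at 0.8 SD, opposing 2-week gap, unadjusted | 40% | 31% | 21% | 15% |
| Power at 0.8 SD, opposing 2-week gap, adjusted | 51% | 54% | 63% | 74% |

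A separate simulation with other assumptions (GA SD 3 weeks, correlation 0.3, 0.5 or 0.7, uncorrected 5% level) agrees in direction. With a 2-week gap, unadjusted false positives were 9%, 17% and 30%; adjusted rates stayed near 5%.

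**Gap by chance alone.** The standard error of the difference in mean GA is 3.46 × √(2/20) = 1.095 weeks. A gap of at least 1 week then occurs in 36% of studies and of at least 2 weeks in 7%. Over all studies false positives stay near 1.7%. If GA spans only 28-34 weeks, the SD is 6/√12 = 1.73 and the standard error 0.55, so a 1-week gap occurs in 7% of studies and a 2-week gap in 0.03%.

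**All IUGR (40) v matched controls (20), 5% level.** Unadjusted false positives are 4.7%, 4.3%, 3.4% and 2.4%, which is conservative. Power at 0.5 SD is about 43% unadjusted and 44%, 47%, 54% and 63% adjusted. Here the loss is precision only, provided the matched IUGR women are typical of the 40.

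**Where adjustment loses.**
- A measure unrelated to GA (R² = 0): power at 0.8 SD falls from 53% to 51% with no gap, and from 54% to 49% with a 2-week gap. The 53% and 54% differ only by simulation noise.
- Narrow window (28-34 weeks, same slope): 53% unadjusted v 52%, 52%, 54% and 59% adjusted.
- GA at scan partly caused by VUE (2-week path, total difference 0.8 SD): the adjusted estimate falls to 0.69, 0.62, 0.51 and 0.43 SD, and power to 37%, 32%, 25% and 24%, against 52-53% unadjusted.

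**The case against.** The strongest reply is that the harm is wholly assumed. Nothing in the documents says that GA differs by VUE status or how strongly any measure depends on GA, and without a systematic gap the planned tests keep their level. That stands, and it limits the point to a conditional one.

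Second, adjustment is not clearly better. Section 1.0 says of VUE that it is not known what activates the T cells, "nor it is understood whether VUE is a cause or an effect of the associated fetal complications", and the scan is tied to IUGR diagnosis. GA at scan may therefore lie on the path from VUE, and adjusting could remove real signal. This also stands; it is why the adjusted model should support the planned tests and not replace them.

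Third, the comparison is inferred. The three groups are never defined, and section 2.1 names normal controls as the comparator. The expected 50% VUE and the mention of three groups make VUE-positive, VUE-negative and control the natural reading, but it remains a reading.

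Fourth, section 7.1 can be read as already comparing GA across groups. It may do so, but seeing a gap does not adjust for it.

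Fifth, the simulated GA effect was linear, so the adjusted model was correct by construction, and controls with VUE were not modelled. Section 7.2 reviews control placentae too, and section 1.1 cites VUE in 30% of all placentae, so some controls may have it. Both limits are fair.

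A reader might infer that the VUE results will be biased, that the comparison with matched controls is biased, or that the plan is in error. The documents support none of these: they show no GA gap, ignoring a genuine match costs precision, and no stated figure is contradicted.

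**Conclusion.** The point holds as a cheap improvement. It is certain from the text that the planned tests use neither matching factor, and that matching at enrolment cannot balance GA between groups defined after delivery. Whether this matters depends on two quantities that the documents do not give. Under the assumptions above, a 2-week gap would raise false positives for the VUE comparison from a nominal 1.7% to about 2-10%; a 1-week gap would do little (1.8-3.3%). With no gap the gain from adjustment ranges from nothing to about 24 points of power (53% to 77%), and it turns into a small loss for a measure unrelated to GA.

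Importance is minor to moderate. In a feasibility study without a power calculation, what is at stake is the reading of exploratory results, not a confirmatory error rate.

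**What to change.** - **Section 15.1 (and 7.1).** Keep ANOVA or Kruskal-Wallis with Dunn's method as the main analysis. Alongside it, prespecify one supporting linear model per continuous measure, on the log or rank scale if residuals require it, with group, GA at ultrasound (continuous) and fetal sex, and multiplicity-corrected pairwise contrasts. For the binary diastolic notch, use a logistic model with group and GA, penalised if events are few.
- **Groups.** Define the three groups by pathology, including how controls found to have VUE are handled.
- **Reporting.** Name GA at ultrasound in section 7.3 and among the variables compared by group.
- **Interpretation.** State in advance that a difference seen only without adjustment may run through GA at scan.

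The cost is analysis-plan wording and one named data item, since the matching already requires GA at ultrasound and fetal sex. Statistically it is two degrees of freedom. Power falls by about 2 points for a measure unrelated to GA, or about 5 points if GA also differs by 2 weeks, and there is little gain in a narrow GA window. Fetal sex itself costs under 1 point if it has no effect (57.2% to 56.5% at GA R² 0.10) and gains about 5 if it explains 10% of the variance (57.3% to 62.2%). The possible removal of real signal, if GA at scan is partly a consequence of VUE, is met by reporting both analyses.

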7.1 Study Methodology

Following consent, women will undergo a comprehensive Doppler ultrasound of the placenta. Prenatal ultrasound is routinely used in clinical practice and considered safe. The ultrasound output level used in this study will be below the FDA limit for fetal imaging. Ultrasound measures to be collected include uterine artery (UtA) and

umbilical artery (UA), systolic/diastolic (S/D) ratio, resistance index (RI), pulsatility index (PI) and presence of early diastolic notch will be collected for each subject.

Additionally, we will explore the benefit of novel ultra-sensitive Doppler technology for microvessel imaging of the placenta. This technology can substantially improve small vessel imaging on ultrasound. A Verasonics ultrasound scanner will be used for ultra-sensitive Doppler imaging. We will collect data on vessel density, periphery-to-center vessel density ratio (VDR), microvessel morphology and the ultrasound attenuation coefficient (UAC). Relevant information about the Verasonics scanner can be found in the Device section.

Maternal and fetal demographics will be collected for all study subjects. Statistical differences between variables in our three groups will be determined ANOVA by Kruskal-Wallis tests if normality is not met. Significance will be defined as a p-value ≤ 0.05 .

7.2 Pathologic Review

In order to confirm VUE diagnosis, placentae will be collected after delivery and placed in formalin. A minimum of 6 samples will be obtained, 2 from cord and membranes and 4 from parenchyma. Placental tissue from the control cohort will then be processed and embedded into paraffin blocks (FFPE) for pathological review for the research study. Placental tissue from the IUGR cohort will be processed and embedded into paraffin blocks (FFPE) for pathological review as per standard clinical pathology protocols. Blocks will be prepped and stained with hematoxylin and eosin for histologic examination by our expert pathologist, [name]. All diagnoses will be based on established and published criteria from the Amsterdam Placental Workshop Group and Society for Pediatric Pathology.¹⁰ Severity, based on immune cell infiltration into the placenta, will be correlated back to ultrasound findings and pregnancy outcome. We will also share de-identified FFPE blocks collected for research only (not clinical residual tissues) with Alpenglow. Alpenglow Biosciences is located in One Discovery Square – Advanced Diagnostics Laboratory. The team will test whether their 3D histology technique can work for placental vascular evaluation (feasibility study).

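### The pathologist whose reading sets the VUE label is not stated to be masked to cohort or ultrasound, and Section 7.2 sends the two cohorts' placentae by different routes

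*Combined protocol and SAP*

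**What the plan says.** Section 7.2 describes two routes. For growth-restricted pregnancies: "Placental tissue from the IUGR cohort will be processed and embedded into paraffin blocks (FFPE) for pathological review as per standard clinical pathology protocols". For controls: "Placental tissue from the control cohort will then be processed and embedded into paraffin blocks (FFPE) for pathological review for the research study". The footnote to the test schedule in Section 4.0 makes no such distinction: "Placenta pathologic sampling and review per clinical protocol".

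Other elements of Section 7.2 are common to both cohorts. Sampling has a floor but no fixed number: "A minimum of 6 samples will be obtained, 2 from cord and membranes and 4 from parenchyma". Staining and reader are shared: "Blocks will be prepped and stained with hematoxylin and eosin for histologic examination by our expert pathologist". So are the criteria: "All diagnoses will be based on established and published criteria from the Amsterdam Placental Workshop Group and Society for Pediatric Pathology".

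Section 7.2 also plans to correlate the severity of infiltration with the ultrasound findings and the pregnancy outcome. Section 7.0 gives the cohort that histology will split: "Forty women will be enrolled after being diagnosed with IUGR", and "Based on our clinical data we expect 50% to have a VUE diagnosis". No section says whether the pathologist is masked to cohort, clinical history or ultrasound. None describes slide labelling, a second reader or an agreement check.

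**The concern.** The primary goal in Section 2.1 is to find out whether Doppler measures predict VUE. Histology is the only reference standard, so it should be read without knowledge of the test it is meant to judge.

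Two features leave that open. First, the placenta is read after delivery and so always after the research scan. Section 1.2 adds that women with IUGR have Doppler monitoring in any case. A reading made in the clinical setting could therefore be made with Doppler findings known. Second, the two cohorts reach the pathologist by different routes, with only a minimum sample number to hold sampling equal.

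If a borderline placenta is more readily called VUE, or graded as more severe, because flow was abnormal, the association between ultrasound and VUE is inflated by the reading itself. If controls are read with less suspicion or from fewer blocks, VUE in controls is under-detected.

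**Working it through.** **Step 1. The two places side by side.**

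| Item | IUGR | Controls |
|---|---|---|
| Route, Section 7.2 | clinical | research |
| Route, Section 4.0 footnote | clinical | clinical |
| Parenchymal samples | at least 4 | at least 4 |
| Reader, stain, criteria | shared | shared |
| Masking to cohort or ultrasound | not stated | not stated |

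The contradiction concerns the controls. The absence of masking concerns everyone.

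**Step 2. Which analyses each gap can reach.** Sections 7.1 and 15.1 compare three groups without defining them. I read them as IUGR with VUE (40 × 0.50 = 20 expected), IUGR without VUE (20) and controls (20).

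- VUE versus no VUE within IUGR: both groups come from one cohort on one route, so a route difference cannot bias this contrast. A reader who knows the ultrasound or clinical findings can.
- Severity correlation: within IUGR the risk is the same. If cohorts are pooled, route and cohort knowledge also matter.
- VUE in controls: exposed to cohort knowledge and to any difference in sampling. At the 30% that Section 1.1 gives for all placentae, 20 × 0.30 = 6 controls would have VUE.

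**Step 3. What unequal sampling could do (illustration only).** The document gives no per-block detection probability *p* and does not say that block counts differ. I assume *p* from 0.1 to 0.5, independent blocks, 4 parenchymal blocks in controls and 8 in IUGR, no false positives, and true prevalence of 30% in both cohorts.

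Detection = 1 − (1 − *p*)^*k*. Apparent gap = 0.30 × (detection at 8 − detection at 4). Control cases missed = 6 × (1 − detection at 4).

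| *p* | *k* = 4 | *k* = 8 | Apparent gap (percentage points) | Missed of 6 control cases |
|---|---|---|---|---|
| 0.1 | 34% | 57% | 6.8 | 3.9 |
| 0.2 | 59% | 83% | 7.3 | 2.5 |
| 0.3 | 76% | 94% | 5.5 | 1.4 |
| 0.5 | 94% | 99.6% | 1.8 | 0.4 |

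**Step 4. Would a four-block cap be a good remedy?** Take *p* = 0.3 and 20 true cases among the 40 IUGR women, again with no false positives.

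- Four blocks: 20 × 0.24 = 4.8 cases fall into the no-VUE group, which becomes 24.8. Then 4.8 / 24.8 = 19%, and the observed difference is about 0.81 of the true one.
- Eight blocks: 20 × 0.058 = about 1.2 cases. Then 1.2 / 21.2 = about 5%, and the difference is about 0.95 of the true one.

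If extra blocks exist, discarding them would dilute the main contrast.

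**Step 5. Bias from unmasked reading.** Nothing in the document allows this to be sized.

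**The case against.** The strongest reply is that Section 7.2 already standardises most of what matters: one expert pathologist, one stain, one published set of criteria and one minimum sample number. The route wording may only separate clinical tissue from research tissue, since the same section restricts sharing of blocks to those collected for research. This is also a small feasibility study with no power analysis. All of that stands, and it limits the point.

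Three stronger readings are tempting, and the document supports none of them.

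- A reader might infer that the pathologist can see the cohort. That rests on separate routes and on silence. The text does not say what is on the slide label or what history reaches the reader.
- A reader might infer that IUGR placentae are sampled more heavily. No section says so. Both cohorts share the same floor, and the eight blocks in Step 3 are an assumption.
- A reader might infer that the route biases every comparison by cohort. It cannot bias the split within IUGR. Comparisons of IUGR with controls, and the computation of the principal components, do not need the VUE label at all.

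Nor should the problem be sized by the usual shrinkage factor 1 − 2*f* (0.90 and 0.80 for assumed error rates of 5% and 10% in each of two equal groups). That describes symmetric random error, which any imperfect reading produces. It does not measure bias from knowing the cohort or the scan.

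What the reply does not answer is the lack of masking. A shared reader and shared criteria do not protect against knowledge of the test result. Feasibility status is a weak defence when Section 15.1 plans significance tests at 0.05.

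**Conclusion.** The concern holds in a limited form. The document routes the cohorts differently in Section 7.2, contradicts this for controls in Section 4.0, and does not mask the one reader who sets the VUE diagnosis and grade. Within IUGR, the exposure is to knowledge of Doppler and clinical findings. For controls and pooled analyses, it is to knowledge of cohort and to any difference in sampling.

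Whether any bias will occur, and how large it would be, is unknown. The 1.8 to 7.3 point gap in Step 3 depends wholly on assumed block counts and detection rates, and shows only that sampling should be held equal and recorded. No sample-size figure changes. The point merits action because the remedy is cheap and protects the reference standard.

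**What to change.** In Section 7.2:

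- State that the study VUE diagnosis and severity grade for all women come from a read by the named pathologist of coded H&E slides in mixed order, without cohort, clinical history or ultrasound results. Keep the clinical report separate.
- Apply the same parenchymal sampling scheme to both cohorts and record the number of parenchymal blocks per placenta.
- Keep any extra blocks in the main diagnosis. Add a sensitivity analysis limited to the four minimum parenchymal blocks, identified as such when they are taken.

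Reconcile the Section 4.0 footnote with Section 7.2, so that one description of the control route remains.

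The cost is slide coding and study re-reads of up to 40 IUGR cases by the same pathologist. No extra reader, tissue or procedure is needed. If that pathologist also made the clinical read, some recall is possible, and masking would then be imperfect for those cases.
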